12.4 Analysis Datasets

Population	Definition
Enrolled	This will comprise all subjects who meet the eligibility criteria and are registered onto the study.
Per Protocol Set (Valid Cases, Efficacy Sample, Evaluable Subjects Sample)	This will comprise all subjects who complied with the protocol sufficiently to ensure that these data would be likely to exhibit the effects of treatment, according to the underlying scientific model. Compliance covers such considerations as exposure to treatment, availability of measurements and absence of major protocol violations. This population should be specifically defined in the protocol.
Treated	This will comprise all subjects who have been exposed to the planned course of treatment to any extent.

12.5 Assessment of Safety

All patients who receive one dose of protocol therapy will be evaluable for assessment of toxicity.

12.6 Assessment of Efficacy

All patients who receive one dose of protocol therapy and are completely resected (rendered NED) will be evaluable for assessment of efficacy.

12.7 Data Analysis Plan

A 2.5% one-sided log-rank test will be used to test the primary hypothesis. The estimation of recurrence free survival and OS will be performed by the Kaplan-Meier product limit method on all patients who undergo complete resection. Descriptive statistics for all outcome measures will be provided. To evaluate the association between variables, either chi-square test (categorical vs. categorical) or two sample t-test (categorical vs. continuous) or correlation (continuous vs.

continuous) will be used depending upon the types of variables in comparison.

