2. STUDY OBJECTIVES

2.1 Primary Objective

Determine if perioperative vaccination with CV301 in combination with nivolumab, systemic chemotherapy and surgical resection improves 3 year OS as compared to perioperative nivolumab, systemic chemotherapy and surgical resection in patients with hepatic-limited metastatic colorectal cancer. Overall survival is defined as time from metastasectomy to date of death from any cause.

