2.2 Secondary Objectives

- Compare 3- year recurrence-free survival (RFS) between the experimental and control treatment groups.
- Compare 3-year OS between the experimental and control groups
- Compare OS (in both the experimental and control groups) to historical controls
- Evaluate the best overall response rates (both by RECIST 1.1 and surgical pathology) between the experimental and control groups.

- Compare the pathologic complete response rate to neoadjuvant therapy in resected tumor tissue between the experimental and control groups.
- In patients who experience a recurrence after surgery, evaluate the proportion of patients amenable to complete re-resection/ablation between the experimental and control treatment groups.
- In patients who experience a recurrence after protocol therapy, compare the progression free survival post-recurrence between the experimental and control groups.
- Evaluate the perioperative surgical outcomes (complications and severity scores) between the experimental and control groups.
- Compare 3-year OS from the date of registration between experimental and control groups

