12.2 Objectives and Endpoints

12.2.1 Definition of Primary Objective and Endpoint

Primary objective: We hypothesize that the addition of vaccination with CV301 to Nivolumab and perioperative systemic chemotherapy followed by complete surgical resection in patients with hepatic-limited metastatic colorectal cancer will significantly increase OS as compared to Nivolumab and perioperative systemic chemotherapy followed by surgical resection.

Primary Endpoint: 3-year OS between perioperative mFOLFOX6 plus Nivolumab and CV301 in combination with surgical resection in patients with hepatic-limited metastatic colorectal cancer. For the primary objective OS is defined as the date of metastasectomy to date of death from any cause.

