12.8 Interim Analysis

The total expected number of deaths is 22 at the end of the follow-up period. A single interim analysis is planned after 14 deaths occur. The purpose of this analysis is to allow an early assessment of efficacy. We shall use a Hwang-Shih-DeCani group-sequential boundary with $\gamma = -4$, yielding an O'Brien-Fleming-like α spending function and a one-sided stopping boundary (30). We expect to spend approximately 0.0052 of the total of $\alpha = 0.025$ at the interim analysis and the remaining 0.0198 at the final analysis. Thus the p-value in the interim must be less 0.0052 to conclude that the two arms are significantly different. At the final analysis the p-value would need to be less than 0.0198 for the two arms to be significantly different.

Power calculations were carried out using Version 1.0 the “gsDesign” package in the R statistical system (R language and environment for statistical computing, R Foundation, Vienna, Austria).

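### The primary endpoint is labelled 3-year OS, but the hypothesis, power and log-rank test concern OS over all follow-up, and the 14-death look usually precedes any 36-month data

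*Combined protocol and SAP*

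**What the plan says.** The combined protocol and SAP describes the primary target in two ways.

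- **As 3-year OS.** Section 2.1 asks whether adding the vaccine to chemotherapy, nivolumab and "surgical resection improves 3 year OS as compared to perioperative nivolumab, systemic chemotherapy and surgical resection". Section 12.2.1 repeats this: "Primary Endpoint: 3-year OS between perioperative mFOLFOX6 plus Nivolumab and CV301".
- **As OS with no time point.** The hypothesis in the same Section 12.2.1 is that adding the vaccine "will significantly increase OS as compared to Nivolumab and perioperative systemic chemotherapy followed by surgical resection". Section 12.3 also speaks of an increase in OS; it uses 58.8% and 88.7% at 3 years as the planning rates and a log-rank test for the 80% power.

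The only deciding rule is the log-rank test. Section 12.7 states: "A 2.5% one-sided log-rank test will be used to test the primary hypothesis". It is not truncated at 36 months. Section 12.8 adds one early look after 14 deaths: "Thus the p-value in the interim must be less 0.0052 to conclude that the two arms are significantly different". On the total it says: "The total expected number of deaths is 22 at the end of the follow-up period".

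The 36-month comparison appears again as a secondary objective in Section 2.2, "Compare 3-year OS between the experimental and control groups", and is mentioned in 12.2.2. Section 12.7 names Kaplan-Meier for estimating OS but gives no method for comparing the arms at 36 months.

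**The concern.** A log-rank test asks whether the hazards differ over whatever follow-up exists at the look. A 3-year OS endpoint asks whether the proportions alive at 36 months differ. The answers can part company in two places. At the interim, the test may succeed before anyone has been observed for 36 months. At the final analysis, the test also counts deaths after 36 months.

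What is at stake is the claim. If the interim boundary is crossed, the objective as worded invites the statement that the vaccine improves 3-year OS, on data that usually contain no 36-month follow-up at all.

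**Working it through.** **Inputs.** 35 resected patients per arm, 3-year OS 58.8% v 88.7%, one-sided 2.5% log-rank (12.3); 14 and 22 deaths, cut-offs 0.0052 and 0.0198 (12.8); 12-month accrual (synopsis). Assumed: exponential survival, uniform entry at metastasectomy and, where a final look is needed, a data cut at month 48.

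**1. The plan's power.** HR = ln(0.887)/ln(0.588) = (−0.1199)/(−0.5310) = 0.226. The Lachin-Foulkes log-rank formula with 3 years' follow-up per patient gives 78.8% at N = 70. The log-hazard-ratio variance with 12-month accrual and 4 years in total gives 80.2%, with 20.7 deaths. The stated 80% is thus reproduced as log-rank power, with the 3-year rates serving to fix the hazard ratio.

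**2. Deaths outside a 36-month endpoint.** By 36 months: 35 × (1 − 0.588) + 35 × (1 − 0.887) = 14.42 + 3.96 = 18.4. Against 22 expected, 22 − 18.4 = 3.6 deaths (3.6/22 = 16%) fall later and still count. With 12-month accrual, 22 deaths are expected at 4.29 years, when every patient has passed 36 months of potential follow-up, so the subtraction is valid.

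**3. Expected time of the 14th death.** Annual hazards: 0.5310/3 = 0.177 and 0.1199/3 = 0.0400. With 1-year accrual, the probability of death by time T after the first metastasectomy is 1 − [exp(−λ(T−1)) − exp(−λT)]/λ. At T = 2.66:
- control: 1 − (0.7454 − 0.6245)/0.177 = 0.317, giving 11.1 deaths;
- vaccine: 1 − (0.9358 − 0.8991)/0.0400 = 0.083, giving 2.9 deaths;
- total: 14.0.

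At T = 2.5 the total is 13.1, which agrees with the synopsis's analysis at 2.5 years if that is timed from the start. With 58.8% in both arms, 14 deaths are expected at 1.77 years. Both times are short of 3 years even for the first patient resected.

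**4. Follow-up at the look (simulation).** Under 58.8% v 88.7%, about 43 to 44% of trials succeed at the interim. No patient has 36 months of potential follow-up in about 76% of all looks, and in nearly all looks if the arms are equal. Accrual matters. Among interim successes, the share in which both arms have a patient followed to 3 years is:

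| Accrual | Share |
|---|---|
| 12 months | 24% |
| 18 months | 35% |
| 24 months | 51% |
| 36 months | 82% |

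**5. How often the rule fires when 3-year OS is equal (58.8% in both arms).**

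| Assumed vaccine-arm hazard | Success at either look |
|---|---|
| Identical curves | about 2% |
| HR 0.7 to month 12, then catch-up by month 36 | 3.1% |
| HR 0.8 to month 24, then catch-up | 3.2% |
| HR 0.5 to month 12, then catch-up | 4.1% |
| HR 0.7 to month 24, then catch-up | 4.2% |
| HR 0.5 to month 24, then catch-up | about 8.5% (7.6 to 8.7% between runs) |
| HR 0.226 to month 18, then catch-up | about 14 to 15% |
| HR 0.226 to month 24, then catch-up | about 25% |

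The catch-up shapes are hypothetical; the documents give no hazard shape.

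**The case against.** The strongest reply is that hypothesis, power calculation and test already agree with one another, and that only the 3-year tag is out of line. Using a 3-year rate to plan a log-rank test is ordinary practice. This stands, and it is why the point concerns the label and the claim rather than the choice of test.

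Four stronger readings are tempting.

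- **That the plan tests the wrong null.** A reader might infer from the endpoint label that the null is equal survival at 36 months. No such null is stated; 12.7 ties the log-rank to the primary hypothesis, which is worded as OS.
- **That the error rate is inflated.** A reader might infer this from the 8.5 to 25% figures. Under proportional hazards the two nulls coincide. The large figures need an early benefit followed by a hazard clearly above control: HR 0.5 for 24 months must be followed by (3 − 0.5 × 2)/1 = 2.0 in the third year. In Section 1.1, the cited vaccine study has median OS not reached against about 44 months, which does not suggest catch-up by month 36. In these shapes survival is also better for part of follow-up, so rejection is not an error for the OS hypothesis.
- **That nothing compares the arms at 36 months.** Sections 2.2 and 12.2.2 list that comparison. Only its method is missing.
- **That 12.8 declares a 3-year result at the interim, or ends follow-up.** It says only that the arms differ, and the study calendar keeps survival status in follow-up. A 3-year claim would come from reading 12.8 together with the objective as worded.

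Nor can 3-year OS be called inestimable at every interim: in about a quarter of looks under the design rates some patient has 36 months of potential follow-up, and with slow accrual most looks would have 36-month data.

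**Conclusion.** The concern holds as an inconsistency between the named endpoint and the analysis that decides it. It changes what the trial may conclude, not whether the log-rank test is valid.

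The wording mismatch needs no assumption. Its practical size rests on the planned 12-month accrual and exponential survival at the design rates: about three quarters of 14-death looks occur with no patient at 36 months, and about 3.6 of 22 final deaths lie beyond 36 months. The first figure falls as accrual lengthens. The firing rates under equal 3-year OS are illustrative only and should not be cited as the trial's type I error.

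**What to change.** - **2.1 and 12.2.1 (and the synopsis):** name the primary endpoint overall survival from metastasectomy, tested by the existing log-rank, with 58.8% v 88.7% kept as planning rates.
- **12.7:** give the listed secondary 3-year OS comparison a method: the difference in Kaplan-Meier 36-month survival with a 95% CI on one prespecified scale (for example log-log), calculated once all resected patients have 36 months of potential follow-up. The scale must be fixed in advance because it matters: estimates of power for such a comparison at 35 per arm run from about 74% (log-log formula) to about 85% (Greenwood, simulated).
- **12.8:** state that an interim crossing supports a conclusion on OS to that date only, and that survival follow-up and the 36-month estimate are completed regardless.

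The cost is wording in these sections and one Kaplan-Meier contrast, with no added patients, events or procedures. The downside is that an interim success cannot be reported as a 3-year OS result until 36-month data exist. The change leaves the log-rank's rejection rates as they are; it limits what is concluded from them.

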2.3 Correlative/Exploratory Objectives

Analyze the following laboratory experiments for biomarker analyses and correlate with response to therapy and clinical outcomes:

- mRNA signature in tumor tissue pre- and post-therapy by whole transcriptome sequencing using RNAseq
- Genomic profiling of metastatic and primary tumor DNA
- CEA and MUC-1 antigen-specific immune response in pre- and post-therapy peripheral blood by intracellular cytokine staining and/or ELISPOT or other validated assays.
- Other tumor-associated antigen-specific immune response measures may be assessed if adequate samples are available
- TCR clonality assays
- Serum cytokine, and serum soluble factors
- PD-1/PD-L1 staining in pre- and post-therapy tumor tissue.
- Immunoscore by IHC

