8: Required biopsies: Timepoints: (1) pre treatment tumor biopsy and (2) tumor biopsy at surgery or for unresectable subjects a fresh biopsy. The goal of collection is 50 mg of tumor tissue to be used for correlative testing. The site investigator and interventional radiologist should discuss the amount of cores that may be necessary to meet the goal of tissue collection. Testing on tumor tissue obtained pre- and post-therapy to include: PD-1 and PD-L1, mRNA signature by whole transcriptome sequencing using RNAseq TCR clonality assays and Immunoscore via IHC. The pre-treatment biopsy is required regardless of prior biopsy confirmation of metastatic CRC. If the subject does not undergo standard of care surgery after pre-surgery treatment, a research specific biopsy will be performed to obtain tissue for research purposes. There will be a cap of 10 fresh biopsies for unresectable subjects. Genomic testing results are required. FoundationOne platform is preferred, however results from an equivalent genomic platform may be used after discussion with the sponsor investigator. Please see the Correlative Laboratory Manual (CLM) for additional details.

9: Required blood collections: Blood will be collected prior to treatment for genomic DNA testing (Day -28 Arm B and Cycle 1 Day 1 Arm A). Testing on peripheral blood pre-therapy and post-therapy to include: Flow Cytometry, including CEA and MUC-1 antigen-specific immune response, and cytokines and serum soluble factors. Timepoints: (1) before vaccination (Arm B)/treatment (Arm A), (2) before surgery, (3) one month after surgery and (4) six months after surgery. In addition, blood for TCR clonality assays will be collected before vaccination (ARM B)/Treatment (ARM A), and 1 month post-surgery. Please see the Correlative Laboratory Manual (CLM) for additional details.

10. Additional pre-operative testing (such as routine pre-admission testing done prior to elective surgery) may be obtained as per institutional guidelines.

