8.2 Peripheral Blood

Patients will have peripheral blood draws for isolation of peripheral blood mononuclear cells (PBMCs). Peripheral blood will be drawn (1) before vaccination on Day -28 (Arm B) or before Cycle 1 Day 1 (Arm A), (2) before surgery (both Arms), (3) one month after surgery for the above-mentioned correlates (both Arms) and (4) six months after surgery (both Arms).

Peripheral blood for PBMCs will be collected and then shipped unprocessed overnight by all participating sites. PBMCs will be isolated. Serum will be collected and shipped for cytokine analysis.

Whole blood will be sent for isolation of genomic DNA for TCR clonality assays before vaccination (ARM B)/Treatment (ARM A), and 1 month post-surgery.

Whole blood will be collected for genomic DNA prior to treatment for both Arms (Day -28 Arm B and Cycle 1 Day 1 Arm A).

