9.7.5 Perioperative Surgical Outcomes

Complications and their severities using the Clavien-Dindo classification for severity scores should be recorded.

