12.2.3 Correlative Objectives and Endpoints

Molecular correlates will also be obtained and descriptive statistics applied.

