12.3 Sample Size and Accrual

This is a 1:1 randomized clinical trial comparing CV-301 vaccine to standard treatment in patients with resectable hepatic metastatic colorectal cancer. Based on a study by Morse et al. [17], the OS probability at 3 years is 0.588. We would like to detect an increase in OS in the CV-301 study arm with 80% power, using a 2.5% level one-sided log-rank test. This survival analysis will be from the time of metastasectomy.

With a sample size of 70 resected patients (35 per study arm), we will have 80% power to detect an increase in the 3-year OS rate from 58.8% to 88.7% using a 2.5% level one-sided log-rank test. Note that the 3-year survival rate of the vaccine treated cohort in the study by Morse et. al. was 92.5%. We will enroll 74 patients, with the expectation that about 5% of the patients will not go on to resection due to either disease progression or complications of neoadjuvant therapy³, leaving us with approximately 70 resectable patients. If the number of unresectable patients is higher than 5%, then we will enroll up to 78 patients.

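### The only test rule for secondary endpoints would by default compare Clavien-Dindo severity between arms with a chi-square test that ignores the order of the grades

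*Combined protocol and SAP*

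**What the plan says.** Section 2.2 lists as a secondary objective: "Evaluate the perioperative surgical outcomes (complications and severity scores) between the experimental and control groups". Section 12.2.2 repeats it, naming both how often complications occur and how severe they are. Section 9.7.5 gives the scale: "Complications and their severities using the Clavien-Dindo classification for severity scores should be recorded".

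Beyond the log-rank test for the primary hypothesis and Kaplan-Meier estimation, the analysis plan has one rule for choosing a test, in 12.7. For associations it prescribes "either chi-square test (categorical vs. categorical) or two sample t-test (categorical vs. continuous"), and correlation when both variables are continuous. Clavien-Dindo is not mentioned there. No rank-based, ordinal or exact method appears in section 12, and no significance level or power is stated for this comparison.

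The size of the comparison follows from 12.3: "With a sample size of 70 resected patients (35 per study arm").

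**The concern.** A Clavien-Dindo grade is a category with a natural order. Under a rule that knows only categorical and continuous variables, arm by grade is most readily read as categorical against categorical, and so as a Pearson chi-square on the full table. That test spreads its sensitivity over every possible difference between the two grade distributions. The difference of clinical interest is a shift toward worse (or milder) grades. The test gives the same result if the grade columns are shuffled. With 35 patients per arm and most patients expected in the lowest categories, many cells are also too sparse for the chi-square approximation.

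This is the trial's between-arm comparison of surgical severity after neoadjuvant vaccination. A non-significant result from a weak test could be reported as reassurance.

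**Working it through.** **The plan's own figure.** The only power stated is 80% for the primary log-rank test. With exponential survival and three years of follow-up for everyone, the hazards are −ln(0.588)/3 = 0.1770 and −ln(0.887)/3 = 0.0400, a ratio of 0.226. The Lachin-Foulkes formula with 70 patients and one-sided 2.5% gives Φ[(√70 × 0.1370 − 1.96 × 0.4117)/0.4247] = Φ(0.80) = 0.788. The 80% therefore reproduces within about a point, and nothing below affects it. There is no stated figure to reproduce for severity.

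**Inputs for severity.**
- From the documents: 35 per arm (12.3), 1:1 allocation (4.1).
- Assumed: two-sided 5%; control grades none/I/II/III/IV/V = 60/12/14/9/4/1%; a common odds ratio (OR) applied to every cumulative split, odds₁(grade ≥ k) = OR × odds₀(grade ≥ k).

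**Example of the shift, OR 2.** Any complication: control 0.40, odds 0.667, doubled to 1.333, so 0.571. Grade II or worse: 0.28 becomes 0.438. Grade III or worse: 0.14 becomes 0.246. Grade IV or worse: 0.05 becomes 0.095. Grade V: 0.01 becomes 0.020. The shifted arm is therefore about 42.9/13.4/19.2/15.0/7.5/2.0%.

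**Sparse cells.** With no difference between arms, expected counts per arm are 35 × (0.60, 0.12, 0.14, 0.09, 0.04, 0.01) = 21.0, 4.2, 4.9, 3.2, 1.4 and 0.35. Five of the six categories are below 5.

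**Power by simulation**, 4,000 trials per setting (Monte Carlo standard error at most √(0.25/4000) = 0.8 points):

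| Analysis | OR 2.0 | OR 2.5 | OR 3.0 |
|---|---|---|---|
| Chi-square, six categories | 15% | 26% | 39% |
| Chi-square, none / I–II / III–V | 24% | 40% | 56% |
| Chi-square, any complication vs none | 27% | 44% | 59% |
| t-test on grade as a 0–5 score | 31% | 50% | 67% |
| Wilcoxon rank-sum | 33% | 51% | 68% |

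With no true difference, the six-category chi-square rejects in 3.6% of trials and the rank-sum in 5.0%.

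The six-category test keeps 15/33 = 45%, 26/51 = 51% and 39/68 = 57% of the rank-sum's power.

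**Sensitivity to the assumed grades.** With seven categories (III split into IIIa and IIIb) and three other control distributions (40%, 55% or 65% without complications), chi-square against rank-sum gives 12–15% vs 31–37% at OR 2, 35–40% vs 67–73% at OR 3, and 57–62% vs 87–90% at OR 4. With five categories it gives 20% vs 35%, 46% vs 70% and 70% vs 88%.

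**Large-sample check.** Suppose all the signal lies in one direction and a 1-degree-of-freedom test has 80% power, so the noncentrality is (1.96 + 0.84)² = 7.85. An omnibus chi-square with the same noncentrality has 71% power on 2 degrees of freedom, 56% on 5 and 52% on 6. The loss therefore comes mainly from the extra degrees of freedom and does not depend on one choice of grade distribution.

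**The case against.** Section 12.7 never assigns Clavien-Dindo to a test; chi-square is an inference from a generic rule. Section 2.2 speaks of severity scores, so an analyst could treat the grade as numeric and take the t-test branch, which loses about a point or two. Section 12.2.2 names incidence alongside severity, so a two-by-two comparison of any complication against none is also within the plan, and it keeps 27/33 = 82% to 59/68 = 87% of rank-sum power. Near-halving appears only if the grades are tabulated uncollapsed. This stands, and it limits the point. It does not remove it, because the plan leaves the choice open and the most literal reading is the weakest one.

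The rank-sum has only about 33% and 51% power at odds ratios of 2.0 and 2.5, so the number of patients is the larger limit. This also stands. The better test improves sensitivity but does not make the comparison well powered.

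The simulations assume a consistent shift across grades, which favours a rank test. A difference that changed direction along the scale could be better seen by chi-square. That is possible, but it is not the shift toward worse severity that matters most here.

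A reader might go further and infer that 12.7 also sends skewed immune markers to an untransformed t-test and discards their baselines. The documents do not support that. Section 12.2.3 says: "Molecular correlates will also be obtained and descriptive statistics applied". Section 2.3 asks for "biomarker analyses and correlate with response to therapy and clinical outcomes", not for a comparison of marker levels between arms. Nothing states that the markers are skewed or rules out a transformation. Pre-treatment blood is collected ("Peripheral blood will be drawn (1) before vaccination on Day -28 (Arm B) or before Cycle 1 Day 1 (Arm A"), section 8.2), but no between-arm marker test is specified that could be said to ignore it.

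**Conclusion.** The point holds for one secondary comparison. By default, 12.7 would give Clavien-Dindo severity a chi-square test that ignores grade order and has sparse cells. Under the assumed 60/12/14/9/4/1% control distribution, 35 per arm and two-sided 5%, power is about 15%, 26% and 39% at odds ratios 2.0, 2.5 and 3.0, against 33%, 51% and 68% for a rank-sum test.

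A reader might take near-halving as a general figure or an upper bound. It is neither. Across the full-grade settings examined, the relative loss runs from about 31% to 62%. It shrinks to roughly 13–27% if grades are collapsed to two or three groups, and nearly vanishes if they are scored. Every distribution and odds ratio is an assumption, since the documents give none. The primary log-rank test and its 80% power are untouched. This is an improvement to consider.

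**What to change.** In section 12.7, state that each patient's highest Clavien-Dindo grade (no complication = 0) is compared between arms by the Wilcoxon rank-sum test, reported with a proportional-odds ratio and 95% confidence interval. Keep chi-square for unordered categories, with an exact test when expected counts fall below 5. The interval matters as much as the test: at 35 per arm it shows how large a worsening remains compatible with a non-significant result.

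Optionally, add that if a marker is ever formally compared between arms, the comparison adjusts for its pre-treatment value on a suitable scale, such as the log. The sampling schedule in the study calendar footnotes (section 7) already provides that value.

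The cost is a changed line of analysis text, best made before outcome data are seen. No new data, visits or patients are needed.
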